5.3 Allocation to Treatment Groups and Blinding/Randomization

Patients will be randomly allocated to either treatment group in a 1:1 fashion. Randomization will be blocked by treatment location (Electrophysiology labs versus other environments due to the differing pad locations in these two environments). A randomization sequence will be created in the RedCAP file. Randomization envelopes will be created and stored in the pre-procedure electrophysiology holding areas or electrophysiology labs or the DCCV procedure areas. In the envelope will be the case report form with the treatment assignment listed on it. Prior to the DCCV procedure staff will open an envelope to learn the treatment assignment and then use the assigned defibrillator. Patients, staff, and investigators will be unblinded. The clinical staff will complete the CRF. They will attach the rhythm strip or ECG acquired 1 minute after the shock and place it back in the envelope. They will seal the envelope and place it in a secure location to be gathered by the study team.

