8.1.2 Screening

Screening will occur immediately before the patient undergoes a DCCV procedure. Screening will be performed by the performing physician investigator. Because the inclusion criteria and exclusion criteria are identical to those for DCCV of AF, no additional chart review will be needed by the physician investigator for study screening. Prior to a DCCV procedure the chart is reviewed and a face to face discussion is had with the patient. These processes will be used to also screen for study inclusion since the same data will be used to determine if they are a candidate for DCCV AND whether they can be included in the study. Screening will occur on site just prior to scheduled DCCV procedures by the investigators performing the procedure. Screening will occur without prior consent/assent/HIPPA authorization under a HIPPA and/or Informed Consent Waiver.

Projected Participants

Recruitment will stop when approximately 560 participants are screened/consented. It is expected that approximately 560 participants will be enrolled to produce 544 evaluable participants.

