11. DATA AND SPECIMEN COLLECTION AND MANAGEMENT

11.1 Data Collection and Management

Data will be collected by study staff on case report forms. The CRF will be completed by the physician investigator at the conclusion of the procedure. The CRFs will be placed in a sealed envelope and stored in a locked file cabinet in the EP lab or CDU care area. The

PI: [name]

study staff will collect the completed forms weekly. The study staff will not need to be present during enrollment or CRF completion. These forms will be scanned and the associated file stored in REDCAP as source documents. Pre and post DCCV monitoring strips or ECGs to document pre DCCV AF and post DCCV rhythm will be stored in PDF format or printed on paper and scanned as source documents into the CRF.

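### The envelope procedure in section 5.3 describes no safeguard that secures allocation concealment, although a REDCap sequence exists from which assignments could be released

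*Combined protocol and SAP*

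**What the plan says.** Section 5.3 holds almost the whole allocation procedure. Assignment is 1:1, blocked by treatment location, with no block size given. The steps are:

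- **Sequence:** "A randomization sequence will be created in the RedCAP file".
- **Storage:** "Randomization envelopes will be created and stored in the pre-procedure electrophysiology holding areas or electrophysiology labs or the DCCV procedure areas".
- **Contents:** "In the envelope will be the case report form with the treatment assignment listed on it".
- **Opening:** "Prior to the DCCV procedure staff will open an envelope to learn the treatment assignment".
- **Blinding:** "Patients, staff, and investigators will be unblinded".
- **After the procedure**, once the form and rhythm strip are inside: "They will seal the envelope and place it in a secure location to be gathered by the study team".

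Section 10.2.1, under the heading on minimising bias, adds only the 1:1 ratio and that codes will not be broken.

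Other sections set the conditions under which the envelopes are used. On eligibility, section 8.1.2 says: "Screening will be performed by the performing physician investigator". On oversight, section 11.1 says: "The study staff will not need to be present during enrollment or CRF completion". Forms are collected weekly. Section 16.1.1 provides an opt-out sheet and no signed consent form. Sections 11.1.1 and 11.3 have paper originals shredded after scanning. Section 5.3 gives completion of the CRF to clinical staff, while section 11.1 gives it to the physician investigator.

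**The concern.** Randomisation protects the comparison only if the person deciding whether a patient enters cannot know, or change, the next assignment. Here the eligibility decision is made immediately before the procedure, at the place where the envelopes are kept, by a clinician who may know how recent patients were assigned. Nothing written ties a particular envelope to a particular patient before it is opened.

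Two things could follow. A patient who looks hard to convert could be left out, or a different envelope taken, once the assignment is foreseen or seen. And an opened envelope could fail to come back, so that a randomised patient is missing from the analysis. Both act on who is in the intention-to-treat population, so analysing that population (section 12.2) does not repair them. First-shock failures are expected in only about 7% of patients, so a modest number of steered cases could matter.

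**Working it through.** **1. Safeguards, set against the text**

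| Safeguard | In the documents? |
|---|---|
| Envelope sealed before use | Not stated; sealing appears only after the CRF is completed (5.3) |
| Opaque, sequentially numbered | Not stated |
| Fixed order of use | Not stated |
| Patient registered before opening | Not stated; no signed consent to fix the time (16.1.1) |
| Log of openings | Not stated |
| Reconciliation of envelopes with the REDCap sequence | Not stated; weekly collection of completed forms only (11.1) |

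Section 8.1.2 expects 560 enrolled to give 544 evaluable, a planned loss of 16 (16/560 = 2.9%). A small shortfall in returned forms would therefore not look unusual by itself.

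**2. Predictability (hypothetical, block design not stated)**

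Assume balanced permuted blocks of size 2m, with the size fixed and known and every earlier assignment in the stratum known. An assignment is certain once one arm's quota in the block is used up. Averaged over all orderings, the certain share is 1/(m + 1). For block size 4, all six orderings can be listed: AABB and BBAA each leave 2 certain assignments, the other four leave 1 each, so (2×2 + 4×1)/24 = 8/24 = 33%.

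| Block size | Share known with certainty |
|---|---|
| 2 | 50% |
| 4 | 33% |
| 6 | 25% |
| 8 | 20% |

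For each size this is an upper bound on the share known with certainty, because it presumes complete knowledge of size and history.

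**3. What imbalance could do (illustration only)**

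From the plan: 93% first-shock success, a 5-point difference of interest, 272 per group (12.2). Assumed: no true difference; two-sided 5% test (alpha is not stated, but the synopsis uses 95% confidence intervals); 25% of patients hard to convert with 81% success, the rest at 97%. Check: 0.25×0.81 + 0.75×0.97 = 0.93.

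If the hard-to-convert share differs between arms by δ, the spurious difference is d = δ×(0.97 − 0.81) = 0.16δ. The type I error is the chance that the observed difference exceeds 1.96×√(2×0.93×0.07/272) = 1.96×0.0219 = 0.0429 in either direction when its mean is d.

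| δ | Spurious difference | Type I error |
|---|---|---|
| 5 points | 0.8 points | about 6.5% |
| 10 points | 1.6 points | about 11% |
| 15 points | 2.4 points | about 19% |
| 20 points | 3.2 points | about 31% |

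A different mix, 70% and 95% success, fits 93% overall only if (0.95 − 0.93)/0.25 = 8% of patients are hard to convert. A 5-point imbalance then gives 0.05×0.25 = 1.25 points, but it means 10.5% against 5.5%, or about 29 against 15 of 272, which is nearly a doubling.

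**4. Sample size**

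The synopsis figure of 538 reproduces: 93% against 98%, two-sided 5%, 80% power, pooled variance, gives 269 per group. With 272 per group (12.2) power is 80.5%. Neither figure depends on how assignments are released, so the change below leaves the sample size as it is.

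**The case against.** Envelopes are an accepted means of concealment, and the envelopes here may well be sealed and numbered in practice. Several stronger readings are tempting and go beyond the text:

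- **That allocation is not concealed.** This would be inferred from silence. What the documents support is that no safeguard securing concealment is described.
- **That the screening physician opens the envelopes with nobody else there.** Section 5.3 says staff open them, and section 11.1 allows study staff to be absent without saying they will be. Clinical staff take part in the procedure.
- **That the same physician records everything.** Sections 5.3 and 11.1 disagree on who completes the CRF. Recording of the outcome is also a separate matter from allocation, and the rhythm strip or ECG is attached as a source document.
- **That lost assignments would go unnoticed.** The sequence sits in REDCap, used envelopes hold a completed form with patient identifiers (11.1.3), and section 16.7 requires reasons for withdrawal to be recorded. A gap could be found. What is missing is a stated step that looks for it.
- **That a third of assignments are foreseeable, or that the bias is a quarter of the 5-point target.** Blocking by location may mean only stratification. The envelopes are used at three hospitals (5.2.1), so complete knowledge of earlier assignments is doubtful. The 1.25-point example needs a near-doubling of difficult patients in one arm.

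These corrections stand and limit the claim. They do not supply the missing safeguards. It is also fair that properly sealed, numbered and logged envelopes would close most of the gap without electronic release.

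**Conclusion.** The point holds in limited form. The procedure in section 5.3, followed as written, would permit assignments to be foreseen, re-drawn or lost. Open-label treatment, screening by the performing physician, optional presence of study staff and the absence of signed consent leave little else to prevent it. Intention-to-treat analysis cannot correct the result.

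The size is unknown. The 20% to 33% predictability range rests on permuted blocks of fixed, known size 4 to 8 and full knowledge of earlier assignments. The 0.8- to 3.2-point spurious differences rest on an assumed patient mix and assumed imbalances. None of these is an estimate for this trial. The documents do not show that bias will occur. They show that nothing described would prevent or reveal it, and that a better method is available at small cost. It should be changed before enrolment.

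**What to change.** 1. **Release from REDCap.** Once eligibility and opt-out status are entered, return a time-stamped assignment from the existing sequence, stratified by location with varying block sizes that are not disclosed to the sites.
2. **Release late.** Do this as close to the DCCV as practicable, so that few randomised patients go unshocked. The synopsis includes ablation patients with only possible DCCV. Since section 9.2.1 connects the patient to the allocated device's pads before sedation, release cannot be later than pad placement. The schedule table, which puts randomisation in the pre-operative column, should be aligned.
3. **Envelopes as backup.** Use sealed, opaque, sequentially numbered envelopes opened in order, with record number and time written on the outside before opening. If envelopes are kept as the main method, this is the minimum.
4. **Reconcile.** At the existing weekly pick-up, match every released assignment to a CRF. Count each as randomised, and state how randomised patients who receive no shock are handled in the analysis.
5. **Consistency.** Reconcile sections 5.3 and 11.1 on who completes the CRF.

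The cost is randomisation-only log-ins for those enrolling, which requires amending the access limits in sections 11.1.2 and 11.3, and a short added step per case. No extra staff are needed, and sample size, treatment, endpoints and the consent model are unchanged.

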6. STUDY TIMELINE

6.1 Individual Participation

The study duration per participant will be up to 1 day. Screening, treatment and the 10 minute follow up will all occur at the time of the planned DCCV procedure.

6.2 Study Timeline

- 6.2.1 Treatment: 1 day
- 6.2.2 Follow-up: same day
- 6.2.3 Estimated Closure: 9-12 months after initiation.

7. PARTICIPANT SELECTION

Participants that do not meet all the inclusion criteria may not be enrolled, unless a prior exception request is approved by the sponsor and submitted for IRB review and approval. Any violations of these criteria must be reported in accordance with IRB Policies and Procedures.

- 7.1.1 Index/Case Participant Eligibility Criteria
 - 7.1.1.1 Age \geq 18 years
 - 7.1.1.2 In AF on presentation with plan for DCCV in either the Electrophysiology lab or DCCV procedure area.

7.2 Exclusion Criteria

- 7.2.1 Index/Case Participant Exclusion Criteria
 - 7.2.1.1 Participants who are receiving any other investigational agents.
 - 7.2.1.2 Parents/guardians or participants who, in the opinion of the Investigator, may be non-compliant with study schedules or procedures.
 - 7.2.1.3 Patients with arrhythmias other than AF
 - 7.2.1.4 Patients with hemodynamically unstable AF
 - 7.2.1.5 Patients with untreated hyperthyroidism
 - 7.2.1.6 Patients with known or suspected pregnancy
 - 7.2.1.7 Patients without sufficient anticoagulation or a transesophageal echocardiogram or computed tomography scan documenting the absence of intracardiac thrombi

7.3 Lifestyle Considerations

- 7.3.1 Not Applicable

7.4 Vulnerable Populations

Vulnerable populations will not be enrolled in this study. Both men and women of all races and ethnic groups are eligible for this trial.

8. RECRUITMENT METHODS

8.1 Methods

8.1.1 Recruitment

Patients in AF presenting to the pre-procedure holding areas prior to DCCV or catheter ablation of AF at Inova care sites will be screened for possible enrollment. Patients will be provided an opt-out information sheet before being enrolled in the study.

8.1.2 Screening

Screening will occur immediately before the patient undergoes a DCCV procedure. Screening will be performed by the performing physician investigator. Because the inclusion criteria and exclusion criteria are identical to those for DCCV of AF, no additional chart review will be needed by the physician investigator for study screening. Prior to a DCCV procedure the chart is reviewed and a face to face discussion is had with the patient. These processes will be used to also screen for study inclusion since the same data will be used to determine if they are a candidate for DCCV AND whether they can be included in the study. Screening will occur on site just prior to scheduled DCCV procedures by the investigators performing the procedure. Screening will occur without prior consent/assent/HIPPA authorization under a HIPPA and/or Informed Consent Waiver.

Projected Participants

Recruitment will stop when approximately 560 participants are screened/consented. It is expected that approximately 560 participants will be enrolled to produce 544 evaluable participants.

8.2 Materials

Not applicable

8.3 Underrepresented Populations

Patients of all races, ethnicities, and sexes will be enrolled.

9. STUDY PROCEDURES

9.1 Screening Visit

9.1.1 Informed Consent/Assent/HIPAA Authorization

We will seek an alteration of consent, a waiver of documentation of consent, and an alteration of HIPPA for this study.

9.1.2 Physical Exam

Not Applicable

9.1.3 Vital Signs

Heart rate and blood pressure before and after DCCV will be obtained. Patients

A Pragmatic Randomized Clinical Trial Comparing Rectilinear Biphasic Waveform and Biphasic Truncated Exponential Waveform Shocks for Cardioversion of Atrial Fibrillation (Zoll vs Lifepak-RCT) |

PI: [name]

with hypotension and tachycardia will be deemed to have hemodynamically unstable AF and will be excluded.

9.1.4 Laboratory Tests

Not applicable

9.1.5 Medical Record Review

This will be performed as part of the screening procedure prior to providing the information sheet.

9.2 Study Intervention Visit

9.2.1 At the study visit the patient will be connected to the randomly allocated defibrillator, connector cable, and pads. Pads will be placed in an anterolateral location unless this is impossible, in which case pads will be applied in alternative locations. After sedation is provided the patient will undergo DCCV at full output (200J for the Zoll Series R device and 360J for the Lifepak Series 15/20 device). After the procedure is complete the pads will be removed and the site assessed for erythema or burns 10 minutes or more after the last administered shock.

9.3 Follow-Up

Not applicable

9.4 Unscheduled Visits

Not applicable

9.5 Lost to Follow-Up

Not applicable

10. STUDY ADMINISTRATION

10.1 Study Intervention(s) Administration

10.1.1 Study Intervention Description

The study will compare safety and efficacy of full output shocks from two commercially available FDA approved defibrillators.

The Zoll R series defibrillator was approved with the following indications on 12/27/2017 (downloaded from www.accessdata.fda.gov on 3/3/2023.)

The R Series System Is Indicated For Defibrillation On Victims Of Cardiac Arrest Where There Is Apparent Lack Of Circulation As Indicated By:1) Unconsciousness;2) Absence Of Breathing; And 3) Absence Of Pulse. The R Series System In The Manual Mode Is Indicated For Synchronized

PI: [name]

Cardioversion Of Certain Atrial Or Ventricular Arrhythmias. A Qualified Physician Must Decide When Synchronized Cardioversion Is Appropriate. The R Series System Semiautomatic And Manual Mode Is Indicated For Use In Early Defibrillation Programs Where The Delivery Of A Defibrillator Shock During Resuscitation Involving CPR, Transportation, And Definitive Care Are Incorporated Into A Medically-Approved Patient Care Protocol. The R Series System Semiautomatic And Manual Mode Is Indicated For Adult And Pediatric Patients.

The Lifepak model 15 and 20 Monitor/Defibrillator was approved with the following indications on 8/22/2018 (downloaded from www.accessdata.fda.gov on 3/3/2023.) Manual defibrillation is indicated for the termination of certain potentially fatal arrhythmias, such as ventricular fibrillation and symptomatic ventricular tachycardia. Delivery of this energy in the synchronized mode is a method for treating atrial fibrillation, atrial flutter, paroxysmal supraventricular tachycardia and, in relatively stable patients, ventricular tachycardia.

10.1.2 Dosing and Administration

The dose of energy for all shocks delivered from the Zoll series R defibrillator will be 200J. The dose of energy for all shocks administered from the Lifepak series 15/20 will be 360J. A patient may receive a second shock at the same output if the first shock is unsuccessful. If the second shock is unsuccessful the original defibrillator and pads will be removed, and the alternate defibrillator applied.

10.2 Measures to Minimize Bias: Randomization

10.2.1 Randomization

Patients will be randomly allocated in a 1:1 fashion to RBW or BTE waveforms and their associated maximal outputs. Randomization codes will not be broken.

10.2.2 Blinding

Neither the investigators nor patients will be blinded to their treatment allocation.

10.2.3 Unblinding

Not applicable

11. DATA AND SPECIMEN COLLECTION AND MANAGEMENT

11.1 Data Collection and Management

Data will be collected by study staff on case report forms. The CRF will be completed by the physician investigator at the conclusion of the procedure. The CRFs will be placed in a sealed envelope and stored in a locked file cabinet in the EP lab or CDU care area. The

PI: [name]

study staff will collect the completed forms weekly. The study staff will not need to be present during enrollment or CRF completion. These forms will be scanned and the associated file stored in REDCAP as source documents. Pre and post DCCV monitoring strips or ECGs to document pre DCCV AF and post DCCV rhythm will be stored in PDF format or printed on paper and scanned as source documents into the CRF.

11.1.1 Storage and Future Use-

All data will be stored in a REDCAP database. Source documents including paper CRF forms will be scanned and files attached to the REDCAP database then shredded.

11.1.2 Retention/Access

Data will be stored in REDCAP according to Inova ORI policy. No specimens will be collected. The study PI and study coordinators will have access to the REDCAP database. Paper case report forms will be stored in a secure location in the procedure area and will be picked up weekly by the study coordinator for entry into the REDCAP database. Records will be retained in the REDCAP registry according to Inova's record retention policy, currently a minimum of 3 years after study completion.

11.1.3 Data Fields

Please see the case report form for exact data collected. Identifiers collected will include name, Inova medical record number, date of birth, and date of DCCV procedure.

11.2 Specimen Collection and Management

Not Applicable

11.3 Security

All data will be stored in a REDCAP database and access will be provided only to the PI and CRC. All paper source documents will be scanned and then the originals will be shredded.

11.3.1 Anonymization, De-Identification and/or Destruction

Data will remain in the REDCAP registry and all analyses will be performed either within the REDCAP registry or on an Inova provisioned computer behind the Inova firewall. No data will be stored outside of REDCAP.

11.4 Release of Locally Banked Data

Not applicable

11.5 Confidentiality

All data and records generated during this study will be kept confidential in accordance with Inova Health System institutional policies and HIPAA on participant privacy. The Investigator and other site personnel will not use such

PI: [name]

data and records for any purpose other than conducting the study.

No identifiable data will be used for future use without first obtaining IRB approval or determination of exemption.

11.5.1 Certificate of Confidentiality

Not applicable

12. DATA ANALYTICS

12.1 Study Endpoints

Efficacy assessments for the primary endpoints will occur using data obtained at screening and the DCCV study visit. Specifically, the endpoint of NSR will be acquired by monitoring strip or 12 lead ECG 1 minute after each DCCV shock is delivered.

Primary Endpoints

- 12.1.1 The frequency of NSR one minute after a single full output DCCV shock is delivered by a Zoll Series R RBW waveform defibrillator and a Lifepak Series 15/20 BTE waveform defibrillator.
- 12.1.2 The frequency of NSR one minute after the first or second full output DCCV shock is delivered by a Zoll Series R RBW waveform defibrillator and a Lifepak Series 15/20 BTE waveform defibrillator.
- 12.1.3 The frequency of NSR one minute after the first or second full output DCCV shock is delivered by a Zoll Series R RBW waveform defibrillator and a Lifepak Series 15/20 BTE waveform defibrillator after crossing over from the alternative defibrillator after failing 2 consecutive full output shocks at maximum output.

Secondary Endpoints

- 12.1.4 The frequency of adverse events including skin irritation, pain, or burning; arrhythmic events including asystole, atrioventricular block, transient bradycardia or ventricular arrhythmia within 10 minutes of the last DCCV shock; and the frequency of pacemaker or ICD dysfunction after shock among patients with prior pacemaker or defibrillator implant. Transient bradycardia will be defined as symptomatic bradycardia requiring the use of temporary pacing, atropine, isuprel, or epinephrine for rate support. The secondary safety endpoint will be assessed only among patients who do not cross-over from one defibrillator to the other.

